#### **4.4 WITHDRAWAL CRITERIA**

This is a retrospective study and therefore there are no withdrawal criteria, in addition to the inclusion and exclusion criteria.

## **5. ASSESSMENT AND FOLLOW-UP**

This is a retrospective data study and therefore there will be no follow-up. Therefore, there will be no assessments.

As all clinical data will be anonymised, incidental findings will not be reviewed or reported back to individuals or their GP or clinical care teams.

The study will end when the last pseudo-anonymised image has been segmented and ECG feature extracted, and the deep learning algorithm has been trained and validated.

## **6. STATISTICS AND DATA ANALYSIS**

Machine learning algorithms will be trained to differentiate between patient groups (e.g. based on diagnosis or prognosis). For example, for the ECG analyses, in addition to conventional morphological features of QRS, we propose to analyse both temporal and spectrum features of the 12-lead ECG. The spectrum features would include band-powers of different frequency bands, and coefficients of auto-regression (AR) models of different orders would be used as temporal features. Moreover, the temporal stability of features (i.e., how the features vary from beat to beat) and the spatial dispersion of these features (i.e., who the features vary across the 12 leads) will also be investigated.

Data will be analysed by the chief investigator and the research team at the National Heart and Lung Institute, Imperial College London. Anonymised data may be shared with collaborators, for example at University College London, for data processing subject to any required data sharing agreements/approval being in place before the data is transferred.

Data and all appropriate documentation will be stored for a minimum of 10 years after the completion of the study, including the follow-up period.

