### 1.2 RATIONALE FOR CURRENT STUDY

Coronavirus Disease 2019 (COVID-19) has been widespread worldwide since December 2019. It is highly contagious, and severe cases can lead to acute respiratory distress or multiple organ failure and ultimately death. The disease can be confirmed by using the reverse-transcription polymerase chain reaction (RT-PCR) test. ECGs, Chest x-rays and CT scans are rich sources of data that provide insight to disease that otherwise would not be available. Knowing who to admit to the hospital or intensive care saves lives as it helps to mitigate resource shortages. Novel Artificial Intelligence tools such as Deep learning will allow a complex assessment of the Imaging and clinical data that could potentially help clinicians to make a faster and more accurate diagnosis, better triage patients and assess treatment response and ultimately better prediction of outcome.

Our group has significant experience implementing machine learning algorithms on vast quantities of ECGs, such as from the UK Biobank, and propose to extend our techniques to data from patients with Covid-19.

ECGs are routinely performed on unwell patients presented to hospital and often have serial recordings during their inpatient stay. This provides a unique method by which disease progression can be tracked using a simple, non-invasive and inexpensive method throughout the course of the illness. Furthermore, whether COVID-19 causes specific ECG changes is not known. Identifying and understanding ECG changes related to COVID-19, particularly those features that may predict clinical outcomes, would be especially useful. The non-invasive, quick and easy nature of recording ECGs in unwell patients makes it an ideal modality to investigate and predict COVID-19 related outcomes.

As the manifestation of COVID-19 and related complications on ECG is currently unknown, we hypothesise that beyond routine radiographic imaging, ECG can provide an insight into clinical outcomes related to COVID-19 that can be helpful for prognostication.

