Imaging of COVID-19 is performed with CXR and CT. Chest radiograph is the initial screening imaging tool in patients with suspicious clinical symptoms of COVID-19 (including fever and lymphopenia). Radiographic appearances are of symmetric patchy or diffuse airspace opacities. Typical CT appearances include peripheral, bilateral ground glass opacity (GGO) which may have a rounded morphology, with or without consolidation. A crazy-paving pattern can be seen with ground glass opacity and intralobular lines. Imaging features depend on when infected patients are imaged. Up to approximately 50% of patients with COVID-19 infection may have normal CT scans 0–2 days after onset of flu-like symptoms [18]. GGO opacity usually develops between day 0 and 4 after symptom onset. The frequency of consolidation increases later in the course of the disease, peaking at 6–13 days with higher rates of bilateral and multilobar involvement. An organising pneumonia pattern is observed with reverse halo or atoll sign and perilobular opacities. About 2–3 weeks after the onset, CT may show varying degrees of clearing of the patchy consolidative opacities, reticular opacities, bronchial wall thickening, and interlobular septal thickening [9]. Imaging (CXR & CT) may be used as an aid in diagnosing COVID-19, guide individual patient management decisions, deal with complications or look for an alternative diagnosis.

With the development of machine learning, deep learning based artificial intelligence (AI) technology has demonstrated tremendous success in the field of medical data analysis due to its capacity of extracting rich features from imaging and complex clinical datasets [10]. Recently, deep learning has been used for diagnosing and distinguishing bacterial and viral pneumonia from thoracic imaging data [11]. In addition, attempts have been made to detect various ECG and chest CT imaging features [12]. In the current COVID-19 pandemic, some preliminary studies have shown promising results for the ECG, chest CT and CXR data analysis and classification [2][3][13]. Besides, small scale initial studies have been done for COVID-19 monitoring [14], screening [15] and prediction of the hospital stay [16].

Exploring the added value of artificial intelligence-assisted disease detection and characterisation may potentially help clinicians to make a prompt correct diagnosis, guide treatment and predict prognosis.

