## 2. STUDY OBJECTIVES

### Primary objectives

- We will investigate if the standard electrocardiogram (ECG), which is a conventional clinical tool used record the electrical activity of the heart, a chest X-ray and/or a CT scan, can be used to predict the course and severity of disease in patients with Coronavirus Disease 2019 (COVID-19).

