### Secondary objectives

- We will also investigate if the standard electrocardiogram (ECG), which is a conventional clinical tool used to record the electrical activity of the heart, a chest X-ray or a CT scan, can be used in patients with Coronavirus Disease 2019 (COVID-19) to predict subsequent heart involvement due to the infection.
- We will assess if computer-based analyses are better than doctors at diagnosing features of COVID-19 infection.

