#### 3.1 STUDY OUTCOME MEASURES

The accuracy with which computer based analysis (machine learning) can diagnose and/or prognosticate Covid-19 infection primarily from ECG, but also from chest xray and CT images.

To determine if computer based analysis (deep learning) enables assessment of the effect of COVID-19 on heart function.

To determine if AI system is superior to cardiology/medical team and/or radiologist assessment.

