#### 4.3 EXCLUSION CRITERIA

The presence of any of the following will preclude the patient from the study:

1. Suboptimal ECGs, chest radiographs or CT studies for deep learning methods due to artefacts including severe motion artefacts which causes blurring of the contours of or significant artefacts due to metallic prosthesis which causes image degradation
2. Time-interval between ECGs, chest CT and the RT-PCR assay was longer than 7 days

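### The prognostic analyses have no index time and no rule that an ECG, chest X-ray or CT must precede the in-stay event it is meant to predict

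*Combined protocol and SAP*

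**What the plan says.** The primary objective (section 2) asks whether an ECG, chest X-ray and/or CT "can be used to predict the course and severity of disease in patients with Coronavirus Disease 2019 (COVID-19". A secondary objective asks whether they can be used "to predict subsequent heart involvement due to the infection". Section 3.1 puts the ECG first: the outcome measure is the accuracy with which machine learning can "diagnose and/or prognosticate Covid-19 infection primarily from ECG, but also from chest xray and CT images".

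Section 6 is the whole analysis plan. On modelling it states "Machine learning algorithms will be trained to differentiate between patient groups (e.g. based on diagnosis or prognosis" and then describes morphological, spectral and temporal ECG features. It does not say at what time a prediction is made, which recording is used when a patient has several, or that the recording must come before the outcome.

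One rule relates the time of a recording to another event in the illness, the second exclusion in section 4.3: "Time-interval between ECGs, chest CT and the RT-PCR assay was longer than 7 days". Section 4.1 lists the clinical and laboratory data to be recorded, some with dates and some without. Section 1.2 notes that inpatients often have repeated ECGs, through which "disease progression can be tracked using a simple, non-invasive and inexpensive method throughout the course of the illness".

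**The concern.** A model that predicts an event should see only what was known before the event. If some training and test recordings were made afterwards, the model can learn to recognise the event or its treatment (a ventilated patient, an injured heart) instead of forecasting it. Accuracy measured that way would tend to be too high, and it would not carry over to the use described in section 1.2, which is deciding whom to admit to hospital or intensive care. At that moment only pre-event recordings exist.

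The plan itself accepts that timing changes what a recording shows. Section 1.2 says of CT and X-ray that "Imaging features depend on when infected patients are imaged" and that "The frequency of consolidation increases later in the course of the disease". It gives no comparable timeline for the ECG.

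**Working it through.** The plan gives no figure to reproduce here, so the check sets the sections side by side.

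**1. Does any section fix the order?**
- Section 2 gives the aim. The word used for heart involvement in the secondary objective implies an order, but nothing puts it into operation.
- Section 6 has no index time and no ordering rule.
- Section 4.3, exclusion 2, measures distance from the RT-PCR test, not from the outcome. It states no direction and does not name chest X-ray. Section 4.2 also admits patients on clinical suspicion, who may have no RT-PCR result to anchor it.

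No other section supplies the rule.

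**2. Can a post-event recording pass every written rule?** Take a hypothetical patient with RT-PCR on day 0, intubation on day 2 and an ECG on day 5. The gap between ECG and RT-PCR is 5 − 0 = 5 days, which is within 7, so the patient is not excluded. The ECG was made 5 − 2 = 3 days after intubation. Nothing stops it being used to predict intubation.

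**3. Can the order be checked from section 4.1?** Both the recording and the event need a listed date.

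| Item | Date listed in 4.1? |
|---|---|
| CT | yes |
| Chest X-ray | yes |
| RT-PCR | yes |
| Intubation | yes |
| Death | yes |
| ECG | no |
| Hospital admission | no (stay in days only) |
| ICU admission | no (stay in days only) |
| Troponin T | no |

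As an illustration, cross three recordings (ECG, X-ray, CT) with three in-stay events (intubation, ICU admission, troponin-based heart involvement), which gives 3 × 3 = 9 pairs. CT and X-ray can be ordered against intubation, so 2 pairs can be checked and 9 − 2 = 7 cannot. If the ECG date needed to apply exclusion 2 is counted as available, ECG against intubation becomes checkable and 6 remain. The choice of events is an assumption, so these counts describe the data list and do not measure bias.

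**4. Can order be inferred without a date?** For some patients, yes.
- Let intubation fall *t* days after RT-PCR. Exclusion 2 keeps the ECG within 7 days of RT-PCR, so the ECG must precede intubation when *t* > 7. For *t* between −7 and 7 the order is open.
- ICU admission can be back-calculated as death date minus ICU days only for a patient with a single ICU stay that ended in death. Survivors have no anchor date.

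**The case against.** The strongest reply has four parts.

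- **Intent is clear.** The stated use is triage, the secondary objective speaks of later heart involvement, and section 4.1 records an early-warning score on arrival and symptom duration at the first visit. These point to a baseline at presentation. That is fair, and it may make post-event recordings less common, but none of it is a rule.
- **The dates exist.** Exclusion 2 cannot be applied without ECG dates, and section 4.1 is a list of clinical and laboratory data that does not claim to describe the ECG and image files. This stands. A reader might infer that investigators could never establish the ECG order. The documents show only that the date is not on the list.
- **Serial ECGs are rationale.** Section 1.2 describes repeated ECGs as an opportunity. Sections 3, 4 and 6 do not commit to analysing them, and the temporal stability in section 6 is beat to beat. This also stands. The concern needs only that repeated recordings exist and that no rule selects among them.
- **The outcomes are not named.** The objectives name neither intubation nor ICU admission as an outcome, and troponin as the heart measure is an assumption. A reader might take seven of nine as a finding about the protocol; it is only an illustration.

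A reader might also try to size the bias from the width of the RT-PCR window. That does not work. Spread around a swab is a different matter from a recording that follows the outcome, and the exclusion can be read in more than one way.

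**Conclusion.** The concern holds for non-fatal events that occur during the stay. The objectives are predictive, the written rules admit recordings made after the event, and for most such events the order cannot in general be checked from the listed variables, including for the ECG, the leading modality. The likely direction is inflated apparent accuracy. The size cannot be derived, because the documents give neither event rates nor the share of recordings made after an event.

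This rests on two assumptions: that course and severity will include events such as intubation or ICU admission, both of which appear in section 4.1, and that heart involvement will be judged by a measure such as troponin.

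A reader might infer that all prognostic results are compromised. The documents do not support that. A recording made in life precedes death whatever the rule, so mortality is affected only through lead time. Discharge follows an in-stay recording in the same way. Diagnostic analyses do not depend on this order.

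**What to change.** In section 6, for each prognostic analysis:
- name the outcome and define the index time;
- admit only recordings made before the outcome;
- remove from that analysis patients who already have the event at the index time;
- fix before training which recording is used (for example the first, or the last before the event; the choice is the sponsor's);
- report how many patients have no pre-event recording.

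In section 4.1, add four fields: ECG date and time, hospital admission date, ICU admission date, and the date of the measure that defines heart involvement. Intervals from arrival would serve if dates may not be kept. In the illustration above, the ECG, ICU and heart-measure dates make all 9 pairs checkable, and the hospital admission date can anchor the index time. Dates alone are not enough, because the ordering rule is still needed.

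The cost is a short addition to section 6 and four fields from existing hospital records. They are best taken at extraction: section 5 describes the data both as anonymised and as pseudo-anonymised, so it is unclear whether they could be recovered later. The downside is that patients with no pre-event recording leave that analysis and apparent accuracy may fall.

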## **7. REGULATORY ISSUES**

### **7.1 ETHICS APPROVAL**

The Study Coordination Centre has obtained approval from Health Regulator Authority (HRA). The study must also receive confirmation of capacity and capability from each participating NHS Trust before accepting participants into the study or any research activity is carried out. The study will be conducted in accordance with the recommendations for physicians involved in research on human subjects adopted by the 18th World Medical Assembly, Helsinki 1964 and later revisions.

An approval from the National Research Ethics Committee (NRES) will be obtained before the start of any study related procedure and other relevant documents. All correspondence with the NRES will be retained in the Study Files.

## **7.2 CONFIDENTIALITY**

The Chief Investigator will preserve the confidentiality of participants taking part in the study and is registered under the Data Protection Act.

## **7.3 INDEMNITY**

Imperial College London holds negligent harm and non-negligent harm insurance policies which apply to this study.

## **7.4 SPONSOR**

Imperial College London will act as the main Sponsor for this study. Delegated responsibilities will be assigned to the NHS trusts taking part in this study.

## **7.5 FUNDING**

This study is not funded from a specific research grant, and the researchers involved are funded through Imperial College London and Chelsea & Westminster Hospital NHS Foundation Trust.

There will be no payments to research participants or researchers.

## **7.6 AUDITS**

The study may be subject to inspection and audit by Imperial College London under their remit as sponsor and other regulatory bodies to ensure adherence to GCP and the UK Policy Frame Work for Health and Social Care Research.

# **8. STUDY MANAGEMENT**

The day-to-day management of the study will be co-ordinated through Imperial College London, Chelsea and Westminster Hospital NHS Foundation Trust and London North West London University Healthcare NHS Trust.

The investigator will make all study documentation and related records available should an auditor inspection occur. Should a monitoring visit or audit be requested, the investigator will make the study documentation and source data available to the Sponsor's representative. All patient data will be handled and treated confidentially

# **9. PUBLICATION POLICY**

The investigators will publish the findings of the study as conference abstract(s) and in peer-reviewed journals.

